#### **Secondary Outcomes:**

1. Description of the cohort
  - a. Prematurity
  - b. Birth weight
  - c. Sex
2. Facility based deliveries

Facility based deliveries prematurity, sex, will be described using percentage and compared between groups using Chi-square test or Fisher's exact test as appropriate. Number of ANC visits will be described using median with inter-quartile range (IQR) and compared between groups using Mann-Whitney U test. Birth weight will be described using mean with standard deviation and compared between groups using Student's t test or using median with inter-quartile range and compared between groups using Mann-Whitney U test if data have non-normal distribution.

Statistical analysis will be performed using STATA software package. Statistical significance will be considered if  $p$ -value  $< 0.05$

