## 1. SYNOPSIS

Study Title	Design, implementation and assessment of a comprehensive community neonatal health package utilising medical and social interventions	
Internal ref. no.	N/A	
Study Design	Cluster randomised control trial	
Study Participants	The population of Preah Vihear (PVH) province, Cambodia	
Planned Sample Size	
 
293 villages with 586 Village Health Support Group Workers (VHSG)
 
26,500 children born in Preah Vihear over the study period and their parents (5,300 deliveries a year)
 
306 health centre nurses and midwives from 28 health centres and 17 health posts in Preah Vihear
 
30 nurses, 27 midwives and 18 doctors from Preah Vihear Referral Hospital
 
	
Planned Study Period	5 years	
	Objectives	Outcome Measures
Primary	The design, implementation and assessment of a comprehensive community neonatal health package utilising medical and social interventions	A comprehensive community neonatal health package utilising medical and social interventions
Secondary	Reduction of perinatal mortality in PVH province, Cambodia	A one third reduction in perinatal mortality in PVH province, Cambodia
Tertiary	To describe the characteristics of neonates, born in PVH province, Cambodia over a five-year time period	A document that describes the characteristics of neonates, born in PVH province, Cambodia over a five-year time period
	To develop a tool to undertake a full review of neonatal services and capabilities in PVH province, Cambodia	A user-friendly tool to assess neonatal healthcare services A report detailing neonatal services and capabilities in PVH province, Cambodia
	Design a fully comprehensive neonatal healthcare training and implementation package adapted to local need	A locally appropriate neonatal healthcare training and implementation package
	Establish regular VHSG meetings to address areas of concern for the local community with respect to childbirth and the neonatal period	Frequency and attendance rate of participants at the programmes VHSG group meetings

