### **3.3. Study Site**

Preah Vihear is one of the most remote and isolated provinces in Cambodia. The province has a population of around 172,000 people spread out through 293 villages in eight districts. The mainly rural population survive on sustenance farming. Within the province there are 28 government HC, 17 HP, and one referral hospitals. Each HC and HP serves a number of villages and is the first point of access for health care. There are approximately 5,300 recorded deliveries in the province per year (data obtained from PVH provincial health offices).

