## 5. STUDY DESIGN

A cluster randomised study design will be used, with a cluster being defined as a HC administrative group, as defined by the PVH Provincial Health Department. This includes all HC, HP, villages, and villagers in that group.

Pilot: to begin in July 2018, consisting of 4 clusters.

Intervention arm: to begin October 2019, consisting of 10 clusters.

Control arm: all remaining clusters.

Completion: December 2022.

The SBLP will be introduced into the provincial referral hospital during 2018.

The SBLP will be introduced into the new referral hospital during 2022.

The choice of which health centres will be included at each time point will be made using purposive sampling to ensure a mix of health centre characteristics. Characteristics that will be taken into account are the distance from the health centre to the referral hospital and number of villages the HC serves.

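### The shape of the birth-weight data decides between a mean and a median comparison; with thousands of births per arm the switch protects nothing and leaves the effect measure open (low priority, cheap to fix)

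*Protocol*

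**What the plan says.** In section 8.1 of the protocol (Perinatal Mortality, Secondary Outcomes), birth weight is an item under "Description of the cohort", next to prematurity and sex. The default analysis is: "Birth weight will be described using mean with standard deviation and compared between groups using Student's t test". The same sentence then offers a second route, the median with inter-quartile range and the "Mann-Whitney U test if data have non-normal distribution". It names no test, plot or threshold for non-normality. The paragraph closes with a significance rule ("Statistical significance will be considered if" the p-value is below 0.05). The protocol gives no target difference, standard deviation or power for birth weight. It refers to a separate SAP for full details; that document was not available here.

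**The concern.** The rule lets the outcome data choose three things together: the summary shown, the test applied and the quantity compared. A difference in means and a Mann-Whitney comparison answer different questions, so the effect measure for a listed outcome is not settled until the data have been looked at. A normality condition is usually meant to protect a t test in small samples. Here each arm has thousands of births, so it is fair to ask whether it protects anything and what it costs.

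At stake is how one secondary result is read. Birth weights are often recorded to a round figure. If the median route is taken, both arms may show the same median although mean weights differ, and a reader would see no difference where there is one.

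**Working it through.** The protocol states no birth-weight figure to reproduce. Its only related arithmetic, 5,300 × 5 = 26,500 births (Synopsis), is consistent.

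**Births per arm**
- Deliveries: "There are approximately 5,300 recorded deliveries in the province per year" (section 3.3).
- Clusters: the unit is the health-centre administrative group (section 5). The number of groups is not stated; one per health centre gives 28, assumed equal in size.
- Allocation (section 5): 4 pilot, 10 intervention, the rest control, so 28 − 4 − 10 = 14 control. Pilot clusters are left out of the primary analysis (section 8.1, Sample size Calculation); I assume the same here.
- Period: October 2019 to December 2022, 39 months.
- Total 5,300 × 39/12 = 17,225. Intervention 17,225 × 10/28 ≈ 6,152. Control 17,225 × 14/28 ≈ 8,612.

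**Would the switch fire?** Weights were simulated at about 6,150 births. Assumed, not from the protocol: term births with mean 3,050 g and SD 420 g, preterm births with mean 2,200 g and SD 600 g.

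| Simulated weights | D'Agostino rejects | Shapiro-Wilk rejects (first 5,000 values) |
|---|---|---|
| Preterm share 2%, 5%, 8% or 12% | 100% | 100% |
| Purely normal | 5.5% | 1% |
| Purely normal, rounded to 100 g | about 5% | 100% |

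The skew behind the rejections is modest, about −0.2 to −0.7, so a rule based on a histogram or a skewness limit might not fire. On rounded normal data, the choice of formal test alone decides the route.

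**Does the t test need the protection?** With 8% preterm and no true difference, on independent births, the t test rejected in 5.4% of trials and Mann-Whitney in 5.0%. A second set of assumed weights (term 3,050 g, SD 380; preterm 2,150 g, SD 500) gave about 5% for the t test as well.

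**Which test finds more?** Power at two-sided 5%, clustering ignored only so that the tests can be compared:

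| True change | Mean difference | t test | Mann-Whitney |
|---|---|---|---|
| All births shifted | 20 g | 0.68 | 0.72 |
| All births shifted | 25 g | 0.87 | 0.90 |
| All births shifted, purely normal weights | 20 g | 0.81 | 0.78 |
| Preterm share 8% to 6% | 17 g | 0.57 | 0.36 |
| Preterm births only, +250 g | 20 g | 0.71 | 0.31 |
| Preterm share 10% to 8%, second set of weights | 18 g | 0.63 | 0.43–0.46 |
| All births shifted, second set of weights | 18 g | 0.62 | 0.67 |

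The preterm-share row for the second set of weights can be checked by hand:
- Mean difference: 0.02 × (3,050 − 2,150) = 18 g.
- Mixture SD: √[(1−p)·380² + p·500² + p(1−p)·900²] = 477 g at p = 0.10 and 461 g at p = 0.08.
- SE: √(461²/6,152 + 477²/8,612) ≈ 7.8 g.
- Power: Φ(18/7.8 − 1.96) ≈ 0.63.

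**What would the medians show?** With the second set of weights rounded to 100 g and the preterm share at 10% against 8%, the two medians were equal in every simulated trial although the means differ by 18 g. With the first set, rounding and a 20 g shift of all births gave an average median difference of 0.3 g, yet Mann-Whitney power was still 0.71. Rounding blinds the displayed summary, not the rank test.

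**Clustering, for scale.** With no true effect and about 615 births per cluster, both routes rejected in about 31% of trials at an assumed ICC of 0.005, 44–46% at 0.01 and 57–58% at 0.02. A t test on cluster means stayed at 4–7%.

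**The case against.** The strongest reply is that this is a wording preference on a descriptive variable. Birth weight sits beside sex and prematurity, describing neonates is a tertiary objective in section 4, and the main hypothesis concerns mortality. That stands, and it sets the priority.

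Second, both routes are written in advance, and how normality is judged is normally an SAP detail. The missing criterion is indeed no fault by itself. But the protocol fixes the switch, and an SAP that only defined non-normality would keep it.

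Third, a reader might infer that the switch is bound to fire and will hide a real difference. The documents do not support this:
- The trigger is near certain only under a formal test, and none is named.
- Mann-Whitney loses power only for a change confined to small or preterm babies. The programme described in sections 3 and 3.2 is mainly emergency and clinical neonatal care, and nothing there says it should reduce preterm or very small births. For a general shift on skewed weights the rank test is as good or slightly better.
- It is also tempting to say that cluster medians would lose nearly all power, but the protocol specifies no such analysis.

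Finally, the absence of a difference in grams with a confidence interval is not caused by the switch: the t-test route does not promise one either.

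**Conclusion.** The point holds in a limited form. The summary, the test and the quantity compared depend on the observed shape of the data, and at about 6,150 and 8,610 births the condition protects nothing, since the t test keeps its 5% level on skewed, independent weights. The practical harm is an effect measure left open until the data are seen, and medians that can coincide when means differ if weights are rounded. A loss of power (about 0.46 against 0.63) arises only for an assumed lower-tail change, so no general claim that the plan hides a birth-weight effect is justified.

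This rests on 28 equal clusters, exclusion of the pilot, and assumed weight distributions, effects and rounding, none of which the protocol gives for birth weight. The robustness of means and the data-dependence of the rule do not hinge on the exact values.

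Priority is low. Ignoring clustering in the same sentence is the larger fault: it makes false differences likely under either route, and dropping Mann-Whitney for an ordinary t test would not repair it.

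**What to change.** In section 8.1, for birth weight:
- Delete the normality condition and the Mann-Whitney branch.
- State that the arms are compared by the difference in mean birth weight, in grams with a 95% CI, whatever the distribution.
- Name the method, because this paragraph gives no allowance for clusters to borrow: a t test on cluster means, or a mixed model with a correction for few clusters.
- Keep the median and inter-quartile range as description only.

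The cost is one sentence in the protocol and the matching line in the SAP, with no new data. The downside is the loss of a rank test that is slightly more powerful for a uniform shift of skewed weights (for example 0.72 against 0.68 at 20 g).

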#### **Sample size Calculation**

With perinatal mortality rate and a simple parallel cluster randomised trial design, the number of clusters are fixed to the intervention and control arm clusters and the time-frame is fixed to five years. The change in study design has been necessitated by logistical reasons and the post-study power calculations are not relevant. We will report limitations to the power in write-up.

The statistical analysis will remain broadly the same, with the main difference being that we will no longer adjust for the confounding effects of time. The primary analysis will exclude pilot cluster results, and will only be conducted on the intervention and control arm clusters.

Please see the study Statistical Analysis Plan for full details.

### ***Economic Evaluation***

A detailed cost analysis will be carried out to estimate the added resources that are required for the SBLP as compared with standard care. These costs will be combined with estimates for the incremental cost of caring for neonates at the referral hospital if attendance is found to increase, and by modelling the subsequent survival benefits in terms of incremental disability adjusted life years averted. This will indicate whether SBLP are cost-effective as compared to the normal standard of care (control arm).

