	
With the Kingdom of Cambodia, Ministry of Health and the Provincial Health Director of PVH province develop a programme blueprint and implementation strategy for introduction of the developed programme into other locations within Cambodia
	
A programme and implementation plan for the reduction of neonatal mortality that can be used throughout Cambodia

	
To calculate the cost-effectiveness of a neonatal community health programme and the resulting changes in care, as compared to the existing care given in the region
	
A cost effectiveness analysis

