### **Economic Evaluation**

A detailed cost analysis will be carried out to estimate the added resources that are required for the SBLP as compared with standard care. These costs will be combined with estimates for the incremental cost of caring for children at AHC, and HCs if attendance is found to increase, and by modelling the subsequent survival benefits in terms of incremental disability adjusted life years averted. This will indicate whether the SBLP is as cost-effective as compared to the existing standard of care (control arm).

At the time of the newborn health questionnaire, the mother will be asked about any health seeking costs the family incurred for their infant in the first four weeks of life.

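### The two economic evaluation sections cost downstream care on different facilities, and section 8.1 has no place for a fall in referral hospital attendance

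*Protocol*

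**What the plan says.** Economic Evaluation appears as a component of the intervention in Protocol section 3.2 and again under Statistics and Analysis in section 8.1. The two texts are nearly the same.

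- **Programme cost.** Both will "estimate the added resources that are required for the SBLP as compared with standard care".
- **Effect.** Both proceed by "modelling the subsequent survival benefits in terms of incremental disability adjusted life years averted".
- **Comparator.** Both name the control arm.
- **Downstream care, section 3.2.** The programme cost is combined with "estimates for the incremental cost of caring for children at AHC, and HCs if attendance is found to increase".
- **Downstream care, section 8.1.** The programme cost is combined with the "incremental cost of caring for neonates at the referral hospital if attendance is found to increase".

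Section 3.2 adds that "the mother will be asked about any health seeking costs the family incurred for their infant in the first four weeks of life"; section 8.1 does not mention family costs. The Synopsis, like section 4, lists as a tertiary objective the "cost-effectiveness of a neonatal community health programme and the resulting changes in care", compared with existing care in the region.

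**The concern.** Two current sections define one analysis and disagree on which care is costed. An incremental cost-effectiveness ratio has a single numerator. If that numerator can be built from AHC and health centres or from the referral hospital, the plan has not fixed the result, and the choice could be made after the costs are known.

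The condition in section 8.1 raises a second problem. An incremental cost is a difference and can be negative. A rule that admits hospital care only when attendance rises records extra use as a cost but never records reduced use as a saving. The objective has no such restriction.

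The ratio is meant to inform a programme that, according to section 3, is to be introduced elsewhere in Cambodia, so the cost base matters to the intended reader.

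**Working it through.** The economic evaluation states no figure, so there is nothing to reproduce numerically. The check sets the two texts side by side and then writes out what each implies.

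**Step 1: compare the terms.**

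| Item | Section 3.2 | Section 8.1 |
|---|---|---|
| Added programme resources | counted | counted |
| AHC | counted (condition unclear) | not named |
| Health centres | counted if attendance rises | not named |
| Referral hospital | not named | counted if attendance rises |
| Patients | children | neonates |
| Effect | DALYs averted | DALYs averted |
| Comparator | control arm | control arm |

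**Step 2: are these different facilities?** Yes. Section 3.2 describes AHC as a non-governmental teaching hospital. Section 3.3 counts 28 government health centres, 17 health posts and one referral hospital separately. Neither list is a subset of the other, so one section cannot be read as a summary of the other.

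**Step 3: write the two numerators.** Let P be added programme resources. Let A, H and R be the signed differences between arms in cost of care at AHC, health centres and the referral hospital. Let D be DALYs averted. Let I = 1 if attendance at the facility is found to rise, and 0 otherwise.

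- Section 3.2, condition on health centres only: P + A + H·I(H)
- Section 3.2, condition on both: P + A·I(A) + H·I(H)
- Section 8.1: P + R·I(R)

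Under the first reading of section 3.2, the two ratios differ by

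[A + H·I(H) − R·I(R)] / D.

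This is zero only if A + H·I(H) happens to equal R·I(R). Nothing in the protocol makes that so.

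**Step 4: the one-sided condition.** If referral hospital attendance falls, I(R) = 0 and section 8.1 reduces to P, so any saving (R < 0) disappears. The protocol's own aims make a fall possible. Section 4 intends each facility to be equipped to resuscitate and to give continuing neonatal care, which could keep some infants at the health centre. Section 3 says infants needing further care are currently sent to the referral hospital.

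**Step 5: direction of the error.** Counting every level whatever the sign gives P + A + H + R. The shortfall of section 8.1 against this is

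A + H + R·[1 − I(R)].

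Positive A and H would make the section 8.1 ratio too low; a negative R with I(R) = 0 would make it too high. No unit cost, attendance count or DALY input is given, so neither the net sign nor the size can be determined.

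**The case against.** Several stronger readings are tempting but are not supported by the documents.

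- **That both sections count downstream care only if attendance rises.** This is clear only in section 8.1. In section 3.2 the comma after AHC allows the condition to attach to health centres alone, leaving AHC costs unconditional.
- **That inclusion depends on a significance test of attendance.** No such test is stated. The 0.05 threshold in section 8.1 stands in the perinatal mortality analysis and is not linked to costing. The wording can be read simply as an observed rise.
- **That the omission makes the programme look cheaper by some percentage.** Any such figure would need an assumed cost share and would assume that the omitted items are costs rather than savings. The documents support neither assumption.
- **That section 8.1 ignores health centres altogether.** Training, mentoring and equipment delivered there fall under added programme resources in both sections. What differs is the care item.
- **That family costs are wrongly excluded.** Section 3.2 collects them ("the mother will be asked about any health seeking costs the family incurred") and section 8.1 is silent. Costing perspective and cost categories are commonly left to the SAP or an economic plan, so this is mainly missing detail.

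A fair objection also applies to the remedy. Section 5 brings the programme into the provincial referral hospital during 2018, before the intervention arm starts in October 2019. Changes there reach both arms, and a between-arm difference cannot capture them. The birth record listed in section 3.2 has no item on facility attendance, so the remedy may take more than rewording.

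The conflict between the two facility lists stands, as does the silence of section 8.1 on falling attendance. A SAP could settle which list to use but would not remove the contradiction from the protocol.

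**Conclusion.** The point holds as an internal contradiction. Sections 3.2 and 8.1 give different downstream cost bases for one analysis, and the cost per DALY averted depends on which is followed. In section 8.1, lower referral hospital attendance is costed as zero, against an objective that covers resulting changes in care in either direction.

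The size and direction of the effect on the ratio are unknown and cannot be obtained from the protocol. The conclusion rests only on the wording of the two sections and on AHC, the health centres and the referral hospital being separate facilities, which the protocol itself states.

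This is a tertiary objective. The mortality comparison is unaffected. The passages should be reconciled before the costs are analysed.

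**What to change.** Put one identical statement in sections 3.2 and 8.1:

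- Incremental cost = added programme resources, including those at the referral hospital, plus the difference in cost of care at health centres and health posts, the referral hospital and AHC.
- Count that difference whatever its sign, with no condition that attendance must rise.
- Use one patient group in both places.
- Attribute use of the shared hospitals to an arm by the infant's cluster of residence. This matches the residence rule already set for the mortality analysis in section 8.1.
- State as a limitation that programme changes at the referral hospital reach both arms, so the between-arm difference does not reflect them.

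**Cost.** The text change is small. Attendance already has to be measured, because both sections depend on whether it rises, but it must now be tabulated by facility level and cluster of residence. If hospital or health centre records do not carry residence, that item has to be added. The ratio may become less favourable to the programme.

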## **9. DATA MANAGEMENT**

### **9.1. Access to Data**

Direct access will be granted to authorised representatives from the University of Oxford and any host institution for monitoring and/or audit of the study to ensure compliance with regulations.

